### Global health status/QoL

QL - Global health status/QoL (revised) (from 2 items)

### Functional Scales (higher is better functioning)

- PF Physical functioning (from 5 items)
- RF Role functioning (from 2 items)
- EF Emotional functioning (from 4 items)
- CF Cognitive functioning (from 2 items)
- SF Social functioning (from 2 items)

### Symptom Scales (higher is more symptoms, worse functioning)

- FA Fatigue (from 3 items)
- NV Nausea and Vomiting (from 2 items)
- PA Pain (from 2 items)

# Single-Item Symptom Scores (higher is more symptoms, worse functioning)

- DY Dyspnoea
- SL Insomnia
- AP Appetite Loss
- CO Constipation

DI - Diarrhoea

FI - Financial Difficulties

QLQ-C30 Summary Score (higher is better functioning, fewer symptoms)
 C30SUMMARY - QLQ-C30 Summary Score, composed by taking mean of all scores except for QL (Global health status/QoL) and FI (Financial Difficulties).

# 4.8.1.GLOBAL HEALTH STATUS/QoL 4.8.1.1. QL - GLOBAL HEALTH STATUS/QoL (REVISED) (FROM 2 ITEMS)

Table 108: Global health status/QoL

Global health status/QoL	N	Mean(SD)	Median(Min-Max)	p-value (wilcoxon test) compared with baseline
Baseline				
w8				
w16				

# 4.8.2. FUNCTIONAL SCALES (HIGHER IS BETTER FUNCTIONING) 4.8.2.1. PF - Physical functioning (from 5 items)

Table 109: Physical functioning/QoL

Physical functioning/QoL	N	Mean(SD)	Median(Min-Max)	p-value (wilcoxon test) compared with baseline
Baseline				
w8				
w16				

# 4.8.2.2. RF - ROLE FUNCTIONING (FROM 2 ITEMS)

Table 110: Role functioning/QoL

Role functioning/QoL	N	Mean(SD)	Median(Min-Max)	p-value (wilcoxon test) compared with baseline
Baseline				
w8				
w16				

### 4.8.2.3. EF - EMOTIONAL FUNCTIONING (FROM 4 ITEMS)

Table 111: Emotional functioning/QoL

Emotional functioning/QoL	N	Mean(SD)	Median(Min-Max)	p-value (wilcoxon test) compared with baseline
Baseline				
w8				
w16				

### 4.8.2.4. CF - Cognitive functioning (from 2 items)

Table 112: Cognitive functioning/QoL

Cognitive functioning/QoL	N	Mean(SD)	Median(Min-Max)	p-value (wilcoxon test) compared with baseline
Baseline				
w8				
w16				

# 4.8.2.5. SF - Social functioning (from 2 items)

Table 113: Social functioning/QoL

Social functioning/QoL	N	Mean(SD)	Median(Min-Max)	p-value (wilcoxon test) compared with baseline
Baseline				
w8				
w16				

# 4.8.3. Symptom Scales (Higher is more symptoms, worse functioning)

4.8.3.1. FA - FATIGUE (FROM 3 ITEMS)

Table 114: Fatigue/QoL

Fatigue/QoL	N	Mean(SD)	Median(Min-Max)	p-value (wilcoxon test) compared with baseline
Baseline				
w8				
w16				

# 4.8.3.2. NV - Nausea and Vomiting (from 2 items)

Table 115: Nausea and Vomiting/QoL

Nausea and Vomiting/QoL	N	Mean(SD)	Median(Min-Max)	p-value (wilcoxon test) compared with baseline
Baseline				
w8				
w16				

### 4.8.3.3. **PA - Pain (FROM 2 ITEMS)**

Table 116: Pain/QoL

Pain/QoL	N	Mean(SD)	Median(Min-Max)	p-value (wilcoxon test) compared with baseline
Baseline				
w8				
w16				

# 4.8.4. SINGLE-ITEM SYMPTOM SCORES (HIGHER IS MORE SYMPTOMS, WORSE FUNCTIONING) 4.8.4.1. DY - DYSPNOEA (FROM 1 ITEM)

Table 117: Dyspnoea/QoL

Dyspnoea/QoL	N	Mean(SD)	Median(Min-Max)	p-value (wilcoxon test) compared with baseline
Baseline				
w8				
w16				

#### 4.8.4.2. SL - INSOMNIA (FROM 1 ITEM)

Table 118: Insomnia/QoL

Insomnia/QoL	N	Mean(SD)	Median(Min-Max)	p-value (wilcoxon test) compared with baseline
Baseline				
w8				
w16				

#### 4.8.4.3. AP - APPETITE LOSS (FROM 1 ITEM)

Table 119: Appetite Loss/QoL

Appetite Loss/QoL	N	Mean(SD)	Median(Min-Max)	p-value (wilcoxon test) compared with baseline
Baseline				
w8				
w16				

#### 4.8.4.4. CO - CONSTIPATION (FROM 1 ITEM)

Table 120: Constipation/QoL

Constipation/QoL	N	Mean(SD)	Median(Min-Max)	p-value (wilcoxon test) compared with baseline
Baseline				
w8				
w16				

#### 4.8.4.5. DI - DIARRHOEA (FROM 1 ITEM)

Table 121: Diarrhoea/QoL

Diarrhoea/QoL	N	Mean(SD)	Median(Min-Max)	p-value (wilcoxon test) compared with baseline
Baseline				
w8				
w16				

#### 4.8.4.6. FI - FINANCIAL DIFFICULTIES (FROM 1 ITEM)

Table 122: Financial Difficulties/QoL

Financial Difficulties/QoL	N	Mean(SD)	Median(Min-Max)	p-value (wilcoxon test) compared with baseline
Baseline				
w8				
w16				

## 4.9. QLQ-C30 SUMMARY SCORE (HIGHER IS BETTER FUNCTIONING, FEWER SYMPTOMS)

4.9.1.C30SUMMARY - QLQ-C30 SUMMARY SCORE, COMPOSED BY TAKING MEAN OF ALL SCORES EXCEPT FOR QL (GLOBAL HEALTH STATUS/QoL) AND FI (FINANCIAL DIFFICULTIES)

Table 123: QLQ-C30 Summary Score/QoL

QLQ-C30 Summary Score/QoL	N	Mean(SD)	Median(Min-Max)	p-value (wilcoxon test) compared with baseline
Baseline				
w8				
w16				

#### **5. SAFETY ANALYSIS**

In safety population.

Table 124: Overall safety

Cohort
Adverse Events
No
Yes
AE Grade >=3
No
Yes
Toxicity: AE related to Binimetinib
No
Yes
Toxicity: AE related to Encorafenib
No
Yes
Toxicity: AE related to any treatment
No
Yes
Toxicity: AE related to all treatments
No
Yes
Toxicity grade >=3
No
Yes
Toxicity related to Binimetinib grade >=3
No
Yes
Toxicity related to Encorafenib grade >=3
No No
Yes
Toxicity related to all treatments grade
>=3
No
Yes
SAE
No

Cohort Yes

Table 125: Most frequent Toxicity with 5% threshold

Toxicity	Frequency	Percentage (%)

Table 126: Grade of most frequent toxicities with 5% threshold overall

Toxicity No G-UK G-1 G-2 G-3	G-3 G-4	G-5
10XICITY 140 G-011 G-1 G-2 G-0	<del>0-0</del> <del>0-1</del>	 

Table 127: List of toxicities grade >=3 in all patients

Patient Number Cohort AE CTCAE AE Grade AE Related to					
	Patient Number	Cohort	AE CTCAE	AE Grade	AE Related to

Table 128: Most frequent AEs with 5% threshold

AE	Frequency	Percentage (%)

Table 129: Grade of most frequent AEs with 5% threshold overall

AE	No	G-UK	G-1	G-2	G-3	G-4	G-5

Table 130: List of all SAEs

Patient Cohort	AE CTCAE	AE AE AE CTCAE Other Grad Star e Date	AE t Stop	AE AE Relat SAE	AE Intensity	AE Related
		e Date	Date	ed 5/1		to

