## Methodology:

This is a phase II clinical trial, with two cohorts of patients included in parallel, all with melanoma BRAF mutated and brain metastases without previous local treatment in the brain. Cohort 1 will include patients with asymptomatic brain metastases and cohort 2 will include patients with symptomatic brain metastasis.

BRAF mutation status will be tested locally using a validated test before patient inclusion, patients will receive both encorafenib 450 mg/day and binimetinib 45 mg/12 h (twice a day) (COMBO450) until progression disease (PD), toxicity or death. After 56 days of treatment, a contrast enhanced brain MRI and body CT scan will be performed as the first tumour assessment. Depending on the outcome of this image test, patients undergo local radiation treatment (radiosurgery or whole brain radiotherapy (WBRT) as per local radiotherapy oncologist. Encorafenib and binimetinib will be interrupted 24h before radiotherapy and restart 24h after the last dose of radiotherapy. After local treatment encorafenib and binimetinib will be administered at same doses until PD, toxicity or death. After progression, patients will be followed only for overall survival. In the case of COMBO450 is providing a clinical benefit to any patient, treatment could be continued, after agreement with Sponsor.

This study will be carried out following good clinical practices (GCP) guidelines as per European and Spanish regulations for clinical investigations.

Number of patients (planned): At least 63 patients.

Cohort 1: N=48; Cohort 2: N=15.

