#### Statistical methods:

The sample calculation has been done for the **primary endpoint (cohort 1)** and it's based on a Fleming's Single Stage Procedure:

We want to show that the Intracranial response rate by modified RECIST 1.1 before local treatment is superior or equal to the reference value, say, 90=40%. Under the hypothesis to have a response rate under new treatment ( $\pi$ 1) of 60% with  $\alpha$  risk = 5% in one-sided test and a power of 80%, the required sample size is 38 patients.

Finally, if 20% of patients will be lost of follow up, die or progress before day 56 without doing the first tumour assessment (according data published in COMBI-MB study), the initial sample size will be 48 patients, to obtain 38 evaluable patients.

Data of study will be analysed in the following populations:

- ITT: All patients that has been enrolled in the trial
- Evaluable population (PP): All patients fulfilling all eligibility criteria and having at least two valid tumour assessments (baseline and one evaluation MRI or CT-scan) without any protocol deviation that makes the patient invalid for the primary endpoint evaluation.
- Safety population: All patients receiving at least one dose of treatment.

Cohort 2 (N=15) is exploratory and no formal sample calculation has been performed, a descriptive analysis will be performed on the same variables and population as cohort 1 (N=48). The only difference is that the population included will be symptomatic. The efficacy and safety as an overall of both cohorts in conjunction will be also addressed.				

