#### 2. Secondary objectives:

[figure not shown]
- a. Intracranial objective response rate assessed by the investigators using modified RECIST 1.1 before local treatment in cohort 2.
- b. Intracranial objective response rate assessed by the investigators using modified RECIST 1.1 before local treatment in cohort 1.
- c. The duration of the intracranial response in both cohorts assessed by the investigators using modified RECIST 1.1.
- d. The intracranial progression free survival by modified RECIST in both cohorts
- e. Percentage of patients free of intracranial progression according to modified RECIST at 6 (week 24), 12 (week 48) and 24 months (week 96) in both cohorts.
- f. Percentage of patients free of extracraneal progression according to RECIST 1.1 () at 6 (week 24), 12 (week 48) and 24 months (week 96) in both cohorts.
- g. Overall survival in both cohorts.
- h. Percentage of alive patients at 6, 12 and 24 months in both cohorts.
- i. Toxicity of the combination until local treatment in both cohorts:
  - Toxicity of the combination after local treatment in both cohorts.
  - Quality of life in both cohorts.

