#### Non-radiological Assessments

Visible cutaneous lesions must be measured clinically. Digital and standardized photographic images including a ruler for scale as part of the image are recommended for documentation. All clinical assessments must be performed within proximity (± 7 days) of any protocol specified radiographic assessments

**Safety evaluation:** Safety assessments and adverse events include tumour-related, unrelated and treatment-related signs and symptoms. Adverse events will be documented and recorded in the CRF upon patient notification. AEs will be collected from the signing of Informed Consent until the end of treatment visit (30 days after end of treatment) or up to resolution. Classification of toxicity will be done according to the common terminology criteria for adverse events of the National Cancer Institute, version 4.03 (NCI CTCAE v. 4.03).

**PFS follow-up:** Body CT-scan and contrast enhanced brain MRI will be performed baseline and every 8 weeks (+/-1 week) up to 12 months and according to normal practice thereafter **until disease progression**, **independently of the end of treatment reason if it was not the documentation of disease progression**.

**OS Follow-up:** After disease progression all patients will be monitored to determine subsequent antineoplastic treatments and survival. It is recommended to maintain contacts by phone or by other methods every 4 weeks to carry out timely follow-up (up to 24 months or study closure).

**New anti-cancer therapy:** Information on subsequent treatments should include the list of post-treatment treatments, the drugs administered, and the date of initiation and discontinuation of each drug. All data will be recorded in the medical record and in the eCRF.

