# 10. STATISTICS

# 10.1. Sample size calculation

# Sample size calculation:

The sample calculation has been done for the **initially proposed primary endpoint (cohort 1)** and it's based on a Fleming's Single Stage Procedure:

We want to show that the Intracranial response rate by modified RECIST 1.1 before local treatment is superior or equal to the reference value, say, 90=40%. Under the hypothesis to have a response rate under new treatment ( $\pi$ 1) of 60% with  $\alpha$  risk = 5% in one-sided test and a power of 80%, the required sample size is 38 patients.

Finally, assuming that, 20% of patients will be lost of follow up, die or progress before day 56 without doing the first tumour assessment (according data published in COMBI-MB study), the initial sample size will be 48 patients, to obtain 38 evaluable patients.

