#### 10.6. Statistical analysis

For each categorical variable, the results will be summarized by frequencies and percentages. For each continuous variable, the results will be summarized by descriptive statistics such as median, range, and interquartile range or by means, standard deviations and 95% confidence intervals (CIs). For proportions, point estimates and exact 95% confidence intervals will be calculated. For time to event endpoints, Kaplan-Meier estimates at selected time points and corresponding curves will be presented. Time to event is derived relative to the first study treatment administration. Laboratory values will be expressed as the absolute values and as grading (ordinal categorical variables) according to NCI CTCAE v 4.03.

Treatment-emergent AE (AEs starting after the administration of study treatment and up to study completion) will be summarized by system organ class and preferred term. Grading will be presented by type and grade in tables showing frequency and percentage of the within-patient worst grades. In addition, grade ≥3 AEs will be summarized separately. Full analysis details will be outlined in the statistical analysis plan (SAP).

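### SAP section 5 applies a pooled 5% cut-off, with no cohort columns, to its term-level safety tables, so cohort 2 rates by term can be lost; the shells also omit the protocol's treatment-emergent rule

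*Combined protocol and SAP*

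**What the plan says.** **Protocol.** Section 10.6 states: "Treatment-emergent AE (AEs starting after the administration of study treatment and up to study completion) will be summarized by system organ class" and preferred term. It asks for worst grade per patient and a separate summary of events of grade 3 or higher, and gives no frequency cut-off. The secondary objectives include "Toxicity of the combination until local treatment in both cohorts", and the same after local treatment. The synopsis says cohort 2 will be described on the same variables as cohort 1, and that safety will also be addressed for the two cohorts together. Section 8.1 sets the collection window: "AEs will be collected from the signing of Informed Consent until the end of treatment visit".

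**SAP section 5** works in the safety population.
- Tables 125 and 126 cover the most frequent toxicities, and Tables 128 and 129 the most frequent AEs, all with a 5% threshold. A typical title is "Table 126: Grade of most frequent toxicities with 5% threshold overall". The readable columns are term with frequency and percentage, or term with grade. None is for cohort.
- Table 124 (overall counts) is headed by cohort.
- Table 127 (toxicities of grade 3 or higher), Table 130 (SAEs) and, in Annex 1, Table 168 (all toxicities) are patient listings with a cohort column and no cut-off.
- The row labels of Table 124 use toxicity to mean a treatment-related AE.
- Nothing in the section mentions treatment emergence.

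**The concern.** The cohorts are unequal: "Cohort 1: N=48; Cohort 2: N=15". A percentage threshold on the pooled denominator is therefore set mainly by the asymptomatic cohort. A term confined to the symptomatic patients can be common among them and still miss 5% overall. A reader could then not compare term-level rates between cohorts, although toxicity is an objective in both.

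The second gap is the event filter. Restricting to the safety population selects patients, not events. AEs are recorded from consent, and screening can start 28 days before first dose. Unless the treatment-emergent rule is carried into the shells, a programmer working from the SAP alone could include events that began before any drug was taken.

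**Working it through.** **1. Denominator.** The protocol says "Number of patients (planned): At least 63 patients". The cohort 1 figure rests on a 40% reference rate, a 60% target and "risk = 5% in one-sided test and a power of 80%, the required sample size is 38 patients". The one-sample normal approximation gives

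n = [(1.645 × √(0.4 × 0.6) + 0.842 × √(0.6 × 0.4)) / (0.6 − 0.4)]² = 37.1, rounded up to 38.

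Allowing for 20% non-evaluable, 38/0.8 = 47.5, rounded up to 48. Then 48 + 15 = 63. The plan's figures reproduce. I take 63 as the safety denominator, assuming every planned patient is dosed.

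**2. What a pooled 5% means.**
- 3/63 = 4.76%: omitted.
- 4/63 = 6.35%: shown.
- So 3/15 = 20% in cohort 2, with 0/48 in cohort 1, is omitted. One further case in cohort 1 brings the term in.

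**3. Sensitivity to the denominator.**
- At N = 61, 3/61 = 4.92%. At N = 79, 3/79 = 3.80% and 4/79 = 5.06%. From 61 to 79 the smallest count shown is therefore 4.
- At N = 60, 3/60 is exactly 5.0%, and the SAP does not say whether the threshold is ≥ or >.
- At N = 56 to 59, three events exceed 5% (3/59 = 5.08%), and at most 2 of 15 (13.3%) can be hidden.

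**4. Probability of omission at N = 63.** Let X ~ Binomial(15, 0.20) in cohort 2 and Y ~ Binomial(48, q) in cohort 1, independent. The term is omitted if X + Y ≤ 3:

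P = Σ (j = 0 to 3) P(X = j) × P(Y ≤ 3 − j).

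The values of P(X = j) for j = 0, 1, 2, 3 are 0.035, 0.132, 0.231 and 0.250.

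| Cohort 1 incidence q | P(omitted) |
|---|---|
| 0% | 0.648 |
| 2% | 0.425 |
| 5% | 0.193 |
| 10% | 0.038 |

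In the first row, 0.398 comes from observing 0 to 2 of 15, and 0.250 from exactly 3 of 15. The incidences are assumptions; the documents give none by term and cohort.

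**5. A per-cohort rule.** The smallest count reaching 5% is 1/15 = 6.7% in cohort 2 and 3/48 = 6.25% in cohort 1. The 3-of-15 term would be shown.

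**6. What remains visible for an omitted term.**

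| Event | Still named in |
|---|---|
| Treatment-related, any grade | Table 168, by patient and cohort |
| Treatment-related, grade ≥3 | Tables 127 and 168 |
| Serious | Table 130 |
| Non-serious and unrelated, any grade | no readable table; counted only in the aggregate AE rows of Table 124 |

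**7. Treatment emergence.** Protocol 10.6 limits its AE summaries to events starting after dosing, and the SAP shells are silent. The gap affects Tables 128 to 130 and the AE, AE grade ≥3 and SAE rows of Table 124. Tables 125 to 127 and the toxicity rows of Table 124 hold treatment-related events, which an event before first dose should not be.

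**The case against.** The strongest reply is that a most-frequent table is an ordinary display choice beside unthresholded listings. A drug-related event in 3 of 15 patients does not disappear: Table 168 lists it with the cohort, and the denominator is known. Table 124 appears to give aggregate counts by cohort. Protocol 10.6 does not promise AE tables by cohort, and the synopsis also plans a joint safety analysis. All of this stands, and it limits the finding to term-level rates and to non-serious unrelated events.

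The omission probabilities are also sensitive. The 65% needs a term that never occurs in cohort 1, whose patients receive the same drugs at the same starting dose. With 10% incidence there, omission falls to 4%.

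Extraction imposes limits. Table 124 survives only as row labels, only Tables 126 and 129 say overall, and the numbering passes from Table 130 to Table 132. However, the headers of Tables 125, 128 and 129 read cleanly without cohort, while the neighbouring listings show it.

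Two stronger readings are tempting and not supported.
- A reader might infer that the trial could report no notable neurological toxicity in symptomatic patients. SAP 6.2 tabulates headache, epilepsy, motor, sensory, speech and other symptoms for cohort 2 at baseline and two assessments, with no threshold. These are snapshots without grade or causality, but the topic is not left to the 5% tables.
- A reader might infer that events before first dose will be counted, and mostly in cohort 2. The SAP is silent, the protocol definition still stands, and nothing in the documents says where such events would fall.

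**Conclusion.** The point holds as a minor reporting gap. Followed as written, SAP section 5 leaves out of its four term-level tables any term with three or fewer cases among 63 patients, including one affecting 20% of cohort 2, and gives no term-level rates by cohort for the terms it does show. This rests on all 63 planned patients being dosed (any safety N from 61 to 79 gives the same four-patient cut-off) and on the shells having no cohort column that was lost in extraction. For a 20% cohort 2 incidence, omission ranges from about 65% to 4% as cohort 1 incidence goes from 0% to 10%.

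What is lost is the cohort-level rate by term and, for a non-serious unrelated AE below the cut-off, any mention by name, even at grade 3. Separately, the shells do not carry the protocol's treatment-emergent restriction, so events before first dose are not explicitly excluded from the AE and SAE displays. Neither gap touches the efficacy analysis.

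**What to change.** In SAP section 5:

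1. Add cohort 1, cohort 2 and total columns to Tables 125, 126, 128 and 129.
2. Show a term if it reaches ≥5% in either cohort, or if any event under it is grade 3 or higher. Write the inequality out.
3. Apply the treatment-emergent definition of protocol 10.6 to the AE, AE grade ≥3 and SAE rows of Table 124 and to Tables 128 and 129. List events between consent and first dose separately.

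The cost is SAP wording, reprogramming and longer tables. With 15 patients, one case is 6.7%, so every cohort 2 term will be shown. No new data are needed: the Table 130 shell already holds cohort and AE start date.

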#### 6. OTHER ANALYSIS

#### 6.1. Dose analysis

In this section, we analyzed the pattern of Corticosteroids dosage between Assessment 1 and 2 with the aim of observing any changes in Corticosteroids usage during the second tumor assessment. To achieve this, we focused on the active Corticosteroids treatments administered during the initial and follow-up tumor assessments. Therefore, we included only those patients who had at least

one active Corticosteroids treatment during either the first or second tumor assessment.

Table 132: Frequency of Dose in Patients with Corticosteroid Treatment by Assessment

case			
CortiDose			
N			
Mean (95%CI)			
SD			
Median (95%CI)			
Range			

Table 133: Frequencies of Corticosteroid Dose Changes between Assessment 1 and 2

Overall
Dose comparison between Assessment 1 and 2 for each patient
Decreased Dose
Increased Dose
Maintained Dose

Table 134: Dose distribution according Assessment

Dose			
Mean (SD)			
Range			

1. Paired samples t-test

Table 135: Mean Difference in Change between Assessment 1 and Assessment 2

Overall
Dose difference between Assessment 1 and
2
N
Mean (95%CI)
SD
Median (95%CI)
Range

Figure 17: Trends in Assessment Differences

Table 136: List of all analyzed patients with their respective tumor assessment information and ongoing corticosteroid treatment. This includes both treatment and specific tumor assessment information

\*The dose scale (mg) on the vertical axis has been plotted on a logarithmic scale to show trends more clearly.

		Cort		Carti Carti	TumA	TumAs	TumAs	TumA	TumAs	TumA	Evillat Accoc A	ccoccm
Patient	CortiMedication Name	Corti :	CortiStar	Corti Corti	ssmT	smNon	smNon	ssmT s	smNon	ssmN	EVIIIILASSES A	133633111
Number	Name	Dose IUNI	tDate	Stop Ung	argSu	TargLe	TarqSu	argRe	TarqRe	ewLe	rcransment	ent 2
		ts		Date oing	m	sNA	m	en	sp	e	Resp 1 date	date
					1111	3117	1111	οp	эp	 		

